##### **Second step of analysis: Outcome analysis**

The primary outcome model will be a weighted Poisson regression based on stabilized weights. Weighted incidence rates and event rates will be calculated and presented. Further details presented in section 7.3.1.5.

#### 7.3.1.1. General Assumptions for Causal Inference

Observational research relies on causal inference methods when deriving unbiased estimates. Hernán & Robins (2019) list 3 conditions to be met, for the valid use of methods like IPTW: conditional exchangeability, positivity and consistency. Additionally, the no interference assumption between subjects should be met. These conditions make

underlying assumptions about the data to be analyzed and violations of the underlying assumptions can bias the estimates, leading to inaccurate conclusions.

#### **7.3.1.1.1. Conditional Exchangeability**

The conditional exchangeability assumption allows an observational study to be conceptualized as a conditionally randomized trial, where the probability to receive the treatment depends on the covariates, but not on unmeasured variables. Essentially, this assumption leads to the postulation of no unmeasured confounding, and potential outcomes can be treated as Missing at Random (MAR). In practice, verifying the validity of the conditional exchangeability assumption is not possible. While we assume conditional exchangeability within specific groups (such as treatment arms or covariate levels), it's important to recognize that unmeasured factors may still exist. Therefore, we proceed with caution, acknowledging that perfect validation of this assumption is unattainable.

#### **7.3.1.1.2. Positivity**

The positivity assumption specifies that every subject has a probability  $> 0$  to receive either treatment, otherwise no causal inference would be possible. The assumption of positivity will be checked by examining the overlap of the propensity score distribution for both treatment groups graphically. The SAS option WCLOUD will be used within the CAUSALTRT procedure to display weights, and if weights  $> 10$  are observed, the potential for non-positivity will be investigated (see section 7.3.1.4).

#### **7.3.1.1.3. Consistency**

The assumption of treatment consistency specifies that there is no ambiguity defining a treatment (Hernán and Robins, 2020). This assumption is also known by the term “treatment variation irrelevance”.

#### **7.3.1.1.4. Interference**

The assumption of no interference specifies that a potential outcome for any subject does not vary with the treatment assigned to other subjects, i.e., a subject's outcome is not affected by other subjects' exposure to the treatment. In the current study interference is not expected due to the characteristics of the studied disease.

### **7.3.1.2. IPTW Estimation**

#### **7.3.1.2.1. Propensity Score Variables Selection**

A PS model will be defined for IPTW estimation.

The pre-specified variables collected at baseline, considered by medical experts to be potentially important covariates, with respect to both treatment assignment and likelihood of experiencing outcome, are presented in Section 9.9 (Table 4).

Firstly, multicollinearity assumption will be assessed by verifying that there are no two or more variables which are highly collinear. Variance Inflation Factor (VIF) will be

computed by specifying the ‘vif’ option in a PROC REG in SAS (see section 9.10). A VIF higher than 10 indicates co-linearity regarding the concerned covariates. The decision of which covariate(s) to drop, if applicable, will be made based on clinical importance.

Secondly, selected variables will be used as covariates in the SAS CAUSALTRT procedure to fit a logistic regression model and compute propensity scores. The response variable will be the probability of receiving Benlysta at enrollment.

In case the model does not converge, multi-level covariates with sparse counts will be collapsed. If any issues remain thereafter, covariates which generate non-convergence will be removed from the model. In either such case, a corresponding footnote will be added to the corresponding statistical tables.

The propensity score model will be finalized prior to proceeding to estimation of weighted incidence and event rates. An evaluation of all variables used in the PS will be made to allow adjustment prior to the final analysis, considering:

- overlap of the predicted probability of exposure initiation through inspection of graphical and distributional summaries (see section 7.3.1.1.2);
- balancing exposure cohorts through IPTW (Robins et al 2000; see section 7.3.1.2.2);

In addition, the odds ratios of the covariates in the PS model will be reported along with 95% CI and p-value using PROC LOGISTIC to identify PS covariates more associated with the treatment assignment and potentially influencing the weight.

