## 9.9. Appendix 9: Treatment Propensity Score Models Covariates

**Table 4: Treatment Propensity Score Models Covariates**

Variables	Categories/Units	Key covariates*
Year of entry in the study	2013/2014 2015/2016 2017/2018 2019/2020	
Age at baseline	Years	Yes
Sex	Female Male	Yes
BMI	Underweight (<18.5) Normal (18.5 - <25) Overweight (25 - <30) Obese (30 - <40) Extremely obese (>=40)	
Race	Black White Asian Other	Yes
Ethnicity	Hispanic/Latino Not Hispanic/Latino	
Region	US/Canada Europe Other	Yes
Baseline Clinical SLEDAI 2000 score	Score	Yes
Baseline SDI	Score	
SLE duration since diagnosis	Years	
Used corticosteroids for SLE in the past six months	Yes No	Yes
Cardiovascular risk factors	Yes No	
Allergic reactions	Yes No	
Interstitial lung disease	Yes No	
Chronic Obstructive Pulmonary Disease (COPD)	Yes No	
Opportunistic Infection	Yes No	

Variables	Categories/Units	Key covariates*
Any other infection	Yes No	
Autoimmune disorders	Yes No	
Hypogammaglobulinaemia	Yes No	
Cancer	Yes No	
Non-Melanoma Skin Cancer (NMSC)	Yes No	
Family history of cancer	Yes No	
End stage renal failure	Yes No	
Depression and/or anxiety disorder	Yes No	
Suicidal ideation and/or suicidal depression and/or suicidal behavior	Yes No	
Attempted suicide	Yes No	
Dialysis	Yes No	
Transplant	Yes No	
Splenectomy	Yes No	

Treatment propensity score models covariates are collected at baseline.

\* Key covariates will be included in PS models. They are selected based on clinical judgment. If during building the PS model, there is a need to simplify the model specification, retention of key variables will be given priority. Any model simplification involving removal of these key covariates, will require further discussions and alignment with study team prior to implementation.

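### A Yes/No covariate that stops the propensity model converging is removed, and it then leaves the balance check that decides whether the weighted analysis goes ahead

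*SAP*

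**What the plan says.** SAP 7.3.1.2.1 draws its candidates from Table 4 (SAP 9.9) and describes them as "considered by medical experts to be potentially important covariates, with respect to both treatment assignment and likelihood of experiencing outcome".

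The rule for non-convergence has two steps. First: "In case the model does not converge, multi-level covariates with sparse counts will be collapsed". Then: "If any issues remain thereafter, covariates which generate non-convergence will be removed from the model". Disclosure is limited to this: "In either such case, a corresponding footnote will be added to the corresponding statistical tables".

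Table 4 marks six covariates as key (age, sex, race, region, clinical SLEDAI 2000 score, recent corticosteroid use). For these, "retention of key variables will be given priority", and removing one needs alignment with the study team. The other 23 have no such protection.

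Balance is judged on SMDs from the procedure that fits the propensity model, with 0.1 as the guide value (SAP 7.3.1.2.2). SAP 7.3.2 ties the baseline and SMD display to the variables in the model. Under the first step in SAP 7.3.1, no further propensity analysis is done if balance is inadequate. The outcome model carries no baseline covariates (SAP 7.3.3).

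Collinearity has its own rule: "A VIF higher than 10 indicates co-linearity regarding the concerned covariates", and "The decision of which covariate(s) to drop, if applicable, will be made based on clinical importance".

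**The concern.** For a Yes/No covariate, removal is the only step the SAP names. When the cause is that every carrier sits in one exposure group, a variable listed for its link to treatment and outcome is removed because of its link to treatment. The underlying problem is non-positivity: the other group has no comparable patients.

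Removal also takes the variable out of view. Neither SAP 7.3.1.2.2 nor 7.3.2 keeps it in the SMD table, so the stop rule is judged without it. The unadjusted outcome model does not pick it up either. Protocol 8.3.2 says safety analyses will be adjusted for the Appendix 7 confounders. That list includes ESRD/dialysis, transplant, splenectomy, immunoglobulin deficiency and history of cancer, which are the kind of item exposed to this rule. The weighted rates could be presented as balanced when a listed confounder is not.

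**Working it through.** The plan gives no figure on this point and no carrier counts. The steps below use the planned 2,000 and 1,000 patients (Protocol 8.2). Carrier counts, odds ratios and risk ratios are assumptions.

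**1. Which covariates are exposed.** Table 4 has 29 covariates: 4 continuous, 4 multi-level and 21 two-level. Two of the two-level items (sex, corticosteroid use) are key, which leaves 19: ethnicity and 18 Yes/No history items.

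**2. How likely an empty cell is.** If carriers have OR times the 2:1 odds of being in the Benlysta cohort, p = 2·OR/(1 + 2·OR). The chance that all m carriers fall in one cohort is p^m + (1 − p)^m.

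| Carriers | OR 1 | OR 3 | OR 5 |
|---|---|---|---|
| 5 | 0.14 | 0.46 | 0.62 |
| 10 | 0.02 | 0.21 | 0.39 |
| 30 | 0.00 | 0.01 | 0.06 |

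At OR 5 the chance is (10/11)^60 = 0.003 for 60 carriers and (10/11)^100 = 0.00007 for 100. This mainly concerns rare conditions, and more so the stronger the link to treatment.

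**3. What the balance check would show.** With prevalence q in one group and zero in the other, SMD = q/√(q(1 − q)/2).
- 10 carriers in the Benlysta cohort, or 5 in the comparison cohort: q = 0.005, SMD = 0.005/0.0499 = 0.100.
- 30 carriers in the Benlysta cohort: q = 0.015, SMD = 0.015/0.0859 = 0.175.

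If the covariate is removed, weighting leaves this almost unchanged. If it is kept, the carriers' propensity score tends to 1 and their stabilized weight to 2/3. The weighted prevalence with 30 carriers is then 30 × (2/3)/2,000 = 0.010, so SMD = 0.010/0.0859 = 0.116. A simulated data set of 3,000 patients with 30 carriers, all in the Benlysta cohort, gave 0.116 kept and 0.174 removed. Both exceed 0.1, but only the first would be displayed. With 10 carriers the kept value is 0.00333/0.0499 = 0.067.

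The check for weights above 10 (SAP 7.3.1.1.2) does not flag these patients, because their weights are below 1.

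**4. Size of the bias.** If carriers have risk ratio RR for the outcome, the rate ratio is multiplied by 1 + q(RR − 1).
- 10 carriers in the Benlysta cohort: 1 + 0.005 × 1 = 1.005 at RR 2; 1 + 0.005 × 9 = 1.045 at RR 10.
- 30 carriers: 1 + 0.015 × 1 = 1.015; 1 + 0.015 × 9 = 1.135.

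As a yardstick, take serious infection at 5.80 per 100 patient-years. Its half-width in Protocol Table 8-1 reproduces as 100 × 1.96 × √(0.058 × (1/7,773 + 1/3,886)) = 0.93. The bias is 5.80 × 0.005 = 0.03 to 5.80 × 0.045 = 0.26 with 10 carriers, and 5.80 × 0.015 = 0.09 to 5.80 × 0.135 = 0.78 with 30. All are below 0.93.

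**The case against.** The plan has real safeguards. Sparse levels are collapsed first, key covariates are protected, the model is fixed before weighted rates are estimated, and removal is footnoted. Medical history is also tabulated unweighted by exposure group (Tables 9.011 to 9.023), and unweighted rates are reported. These limit the harm, but none shows the weighted imbalance of a removed non-key item or brings it into the stop rule.

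Four stronger readings are tempting, and the documents do not support them.

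- **The collinearity rule does the same.** It does not. VIF is computed from the covariates alone, so it cannot select on separation by treatment. The choice of what to drop is clinical. A VIF above 10 means R² above 0.90, so the retained variables hold most of the information. In the simulation, dropping one of a pair with VIF 17 still left it balanced (SMD 0.246 before weighting, about −0.01 after).
- **Near-separation triggers removal.** For a single Yes/No item an empty cell is needed. With 60 carriers against 1, the lone comparison carrier has a stabilized weight of (1/3)/(1/61) = 20.3. That exceeds 10 and prompts the checks in SAP 7.3.1.1.2 and 7.3.1.3, with the covariate still in the model.
- **The bias could be 6 to 20%.** That follows from 3 to 5% carriers and RR 3 to 5 (1 + 0.03 × 2 = 1.06; 1 + 0.05 × 4 = 1.20), but it needs 60 to 100 carriers all in the Benlysta cohort. Step 2 shows how unlikely that is even at OR 5.
- **Keeping the covariate would cure the problem.** It would not. The SMD with 30 carriers stays at 0.116 because no comparison patient carries the condition.

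One further limit stands. Whether removal happens depends on how the software reports separation. In the simulation the coefficient ran to 22.9 with a standard error near 14,400, yet the routine reported convergence. The SAP does not define non-convergence, so removal is possible but not certain.

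**Conclusion.** The point holds for non-convergence in the 19 two-level non-key covariates. The removal rule, with balance displays tied to the fitted model, allows the stop rule to pass while a listed confounder is unbalanced. SAP 7.3.2 might be read as covering every candidate covariate, but nothing says so.

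The bias per covariate is probably small: 0.5 to 4.5% with 10 carriers and 1.5 to 13.5% with 30, all in the Benlysta cohort, at assumed RR 2 to 10. The same number of carriers in the comparison cohort doubles q (10 carriers: 1 to 9%) and acts in the opposite direction. More than one covariate could be removed. The case for change rests less on the size than on visibility: with 30 carriers in one cohort the weighted SMD is about 0.17 and does not appear in the balance table.

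**What to change.** Amend SAP 7.3.1.2.1, 7.3.1.2.2 and 7.3.2 as follows.

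1. Report unweighted and weighted SMDs for every Table 4 covariate, whether or not it is in the final model, and apply the balance stop rule to that full list.
2. Where a level is empty in one exposure group, treat it as non-positivity. Repeat the weighted tables (54.010 and 54.020) without those carriers and report their number. The covariate is then constant and drops out legitimately. State in advance how the stop rule reads when an empty cell is its only breach.
3. For sparse covariates with carriers in both groups that still fail to converge, use a Firth penalized logistic fit before any removal.

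The VIF step can stay as written.

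The cost is SAP wording, a short macro for the SMDs, one extra set of weighted tables without a few patients (which then describe a slightly narrower population), and slight shrinkage of coefficients where the Firth fit is used.

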#### **7.3.1.2.2. Balance Assessment of the Propensity Score Model**

As described in Rosenbaum and Rubin (1983), the propensity score is also a balancing score. To assess the balance that is produced by a propensity score model, standardized mean differences (SMDs), variance ratios and weighted density plots for the continuous covariates will be displayed using the ‘CovDiffPS’ and ‘PSCovDen’ options in the SAS PROC CAUSALTRT statement in SAS.

The resultant table and plots will be provided as supplementary outputs, presenting SMDs and variance ratios before and after weighting (per SAS ODS table name ‘PSCovDiff’) in order to assess covariate balance after weighting.

An improvement in the covariate balance after weighting would be indicated by the following two observations when the unweighted and weighted columns in the table are compared:

- Smaller SMDs in the weighted column than in the unweighted column
- Variance ratios between 0.5 to 2 in the weighted column

Although there is no universally agreed criterion as to what threshold of the standardized difference can be used to indicate important imbalance, it is commonly agreed that a standardized mean difference of less than 0.1 indicates a negligible difference in the mean

or prevalence of a covariate between treatment groups (Austin, 2011). Of note, variance ratio will be assessed but the main criterion of balance will be based on SMDs.

### 7.3.1.3. Handling of Extreme Weights

Following satisfaction of positivity assumptions as per section 7.3.1.1.2, if there is evidence of extreme weights ( $> 10$ ) that cannot be resolved by adjusting the PS model then subjects in the tails of the propensity score distributions will have their propensity score truncated at the 99th percentile value (i.e.: large weight will be replaced with the 99th percentile).

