This is a multi-center, prospective, observational cohort study to evaluate the incidence of adverse events of special interest (AESI) and effectiveness in patients with active, autoantibody-positive SLE treated with and without BENLYSTA. BENLYSTA refers to any commercially available formulation of belimumab. BENLYSTA formulation, intravenous (IV) or subcutaneous (SC), will be recorded for each patient in the protocol database. Patients will receive BENLYSTA at the discretion of their physician. All treatment decisions are at the discretion of the patient and their healthcare provider and are not mandated by study design or protocol. All assessments are intended to be performed at the time of clinical encounters, per routine care. Patients will be enrolled into 1 of 2 cohorts, those who, at baseline, are receiving or initiating BENLYSTA (BENLYSTA cohort) or are not receiving BENLYSTA (comparison cohort). BENLYSTA or comparison cohort patients may be either treatment initiators or current users. Treatment initiators are defined as those patients who have initiated immunosuppressants and/or BENLYSTA in the last 2 months, while the current users are those who have received immunosuppressants and/or BENLYSTA for ≥ 2 months at the time of entry into the registry. The study will enroll approximately 3,000 patients, approximately 2,000 in the BENLYSTA cohort and 1,000 in the comparison cohort. Enrollment is expected to occur primarily in the US, Canada, and Europe. Each patient will be followed for 5 years contributing a total of approximately 7,773 patient years in the BENLYSTA cohort and 3,886 patient years in the comparison cohort, respectively, assuming a 10% annual patient drop-out rate and not accounting for crossover.

Data will be collected at enrollment and at approximately 6 month intervals for 5 years (60 months). All patients will be assessed for AESI including serious infections, opportunistic infections and other infections of interest, malignancies (including NMSC), selected serious psychiatric events and mortality. Organ damage as assessed by SLICC/ACR Damage Index (SDI), concomitant SLE medications including steroids, demography (eg, age, gender, race/ethnicity; where allowed by local regulation), smoking history, alcohol use,

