##### **First step of analysis: Inverse probability of treatment weighting (IPTW)**

Propensity scores will be computed as the probability of being exposed to Benlysta at enrollment given an individual’s baseline characteristics. Logistic regression will be used to derive the PS. Non-stabilized weights (i.e. IPTW) for each individual will be calculated as the inverse of the probability of receiving the actual exposure:  $1/PS$  for the Benlysta arm and  $1/(1-PS)$  for the Non-Benlysta arm.

Inverse probability of treatment weighting (IPTW) (Rosenbaum, 1983) will be used to adjust for differences in covariates balance between exposure groups, Benlysta versus Non-Benlysta. To reduce likelihood of extreme weights being assigned in the analysis, stabilized weights will be computed by multiplying the non-stabilized weight of each individual by the proportion of subjects who were exposed to Benlysta at enrollment :  $p/PS$  for the Benlysta arm and  $(1-p)/(1-PS)$  for the Non-Benlysta arm., (Chesnaye, 2021). For the remainder of the document, references to “weight” refer to stabilized weights.

These weights will create a *pseudopopulation* whereby confounding factors are balanced among Benlysta and non-Benlysta arms. The weights’ distributions will be checked to identify extreme weights which might impact results (see section 7.3.1.3). If the balance assessment reveals that adequate balance cannot be achieved between the Benlysta and non-Benlysta arms (section 7.3.1.2.2), no further analysis using propensity scores will be conducted.

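### SAP 7.3.1.3 treats two different truncation rules as one, and the rule in its main clause cannot reduce any large BENLYSTA weight

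*SAP*

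**What the plan says.** SAP section 7.3.1 defines the score: "Propensity scores will be computed as the probability of being exposed to Benlysta at enrollment", given baseline characteristics. The unstabilized weight is "calculated as the inverse of the probability of receiving the actual exposure", which is 1/PS for BENLYSTA and 1/(1-PS) for NON-BENLYSTA. Stabilization gives p/PS and (1-p)/(1-PS), where p is the proportion on BENLYSTA at enrollment. From there on, the SAP says, mentions of weight "refer to stabilized weights".

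Section 7.3.1.3 applies after positivity has been judged satisfactory, "if there is evidence of extreme weights" (above 10), and only if adjusting the propensity score model does not resolve them. It then states that "subjects in the tails of the propensity score distributions will have their propensity score truncated at the 99th percentile value". The same sentence glosses this, after an i.e., as "large weight will be replaced with the 99th percentile".

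No lower percentile is named, and the section does not say whether the percentile is pooled or taken within exposure group. The example code in Appendix 10 outputs both the score and the weight and has no truncation step.

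**The concern.** The main clause changes the score; the parenthesis changes the weight. The i.e. presents them as the same thing. Large weights arise at opposite ends of the score in the two groups, so a single upper limit on the score cannot act on both.

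The choice matters because Tables 54.010 and 54.020 are the only confounding-adjusted AESI results listed, and section 7.3.3 plans no covariate adjustment in the outcome step. Several AESI are rare, so one heavily weighted patient with an event can move a rate visibly. Section 7.3.1.2.1 finalizes the propensity score model before weighted rates are estimated, but the truncation step would still be open to two readings at programming.

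**Working it through.** **Inputs from the documents.** The weights are p/PS and (1-p)/(1-PS) (SAP 7.3.1). The trigger is a weight above 10 (SAP 7.3.1.3). The protocol plans "approximately 2,000 in the BENLYSTA cohort and 1,000 in the comparison cohort", so p = 2/3; the realised p is not given. Planned patient-years are 7,773 and 3,886 (Protocol 8.2).

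**Assumption.** The documents give no score distribution. I take logit(PS) as normal with SD 1.0 to 2.5, centred so that the mean PS is 2/3, with N = 3,000. SD 1.0 and 1.5 correspond to c-statistics of about 0.74 and 0.82. There is no plan figure to reproduce for this rule.

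**Step 1, algebra (no distributional assumption).**
- A BENLYSTA weight above 10 needs (2/3)/PS > 10, so PS < 0.067.
- A comparator weight above 10 needs (1/3)/(1-PS) > 10, so PS > 0.967.
- Replacing PS by min(PS, c) can only lower PS. That leaves p/PS unchanged or raises it, so no BENLYSTA weight falls. For example, PS = 0.03 gives (2/3)/0.03 = 22.2 before and after.

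**Step 2, who is affected by a pooled cap.** About 30 of 3,000 subjects lie above the pooled 99th percentile of PS. In the simulation 29 to 30 of them are BENLYSTA subjects, whose weights are already small. The comparators among them average 0.93, 0.18, 0.06 and 0.02 at SD 1.0, 1.5, 2.0 and 2.5.

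**Step 3, simulation.** There were 400 datasets per SD. Each cell gives the mean number of weights above 10 / the mean largest weight.

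| Operation | Group | SD 1.0 | SD 1.5 | SD 2.0 | SD 2.5 |
|---|---|---|---|---|---|
| None | BENLYSTA | 0.04 / 6.0 | 1.06 / 13.3 | 3.29 / 27.2 | 5.29 / 42.5 |
| None | Comparator | 0.41 / 9.9 | 3.31 / 22.3 | 6.48 / 43.0 | 8.10 / 83.8 |
| PS capped above, pooled | BENLYSTA | 0.04 / 6.0 | 1.06 / 13.3 | 3.29 / 27.2 | 5.29 / 42.5 |
| PS capped above, pooled | Comparator | 0.00 / 7.7 | 3.31 / 19.6 | 6.48 / 41.3 | 8.10 / 71.2 |
| PS capped above, by group | BENLYSTA | 0.04 / 6.0 | 1.06 / 13.3 | 3.29 / 27.2 | 5.29 / 42.5 |
| PS capped above, by group | Comparator | 0.00 / 4.0 | 0.00 / 6.0 | 0.69 / 7.5 | 2.43 / 8.5 |
| PS clipped at pooled 1st and 99th | BENLYSTA | 0.00 / 3.6 | 0.16 / 8.6 | 3.29 / 18.4 | 5.29 / 34.2 |
| Weight capped, pooled | Both | 0.00 / 3.1 | 0.00 / 4.4 | 0.00 / 5.3 | 0.00 / 6.0 |

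With two-sided clipping, the comparator results equal those of the pooled upper cap. A separate run restricted to datasets that trigger the rule agrees: under the upper score cap the mean largest BENLYSTA weight stays at 13.7 (SD 1.5) and 26.2 (SD 2.0).

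**Step 4, scale on a rate.** Stabilized weights average about 1, so weighted comparator time is near the planned 3,886 years, and one event with weight w adds about w/38.86 per 100 patient-years. At SD 1.5, if the most heavily weighted comparator has the event, it adds 19.6/38.86 = 0.50 under the pooled score cap and 4.4/38.86 = 0.11 under the weight cap. For BENLYSTA the figures are 13.3/77.73 = 0.17 and 4.4/77.73 = 0.06. The protocol's reference rate for opportunistic infection is 0.136, or about 0.136 × 38.86 = 5.3 expected comparator events. This is an illustration, not a forecast; it ignores the small change that capping makes to the denominator.

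**The case against.** The strongest reply is that the sentence explains itself. The section is about extreme weights, its trigger is a weight, and the parenthesis says the large weight is replaced. A programmer who follows it caps both groups and, with a pooled percentile, leaves no weight above 10 in any scenario tried. This stands. A reader might infer that the weighted rates will retain the outliers; the documents do not establish that, because one of the two stated operations removes them.

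A reader might also infer that comparators are hardly affected by the score cap. That holds only for a pooled percentile with wide score spread. At SD 1.0 the pooled cap already removes the comparator weights above 10. Among comparators the weight rises with PS, so a by-group score cap acts as a by-group weight cap.

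The plural in tails could mean clipping at both ends. But no lower limit is given, and clipping at the 1st and 99th percentiles still leaves every BENLYSTA weight above 10 still above 10 at SD 2.0 and 2.5.

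The rule may also never be used. In a rerun at c = 0.74, no weight exceeded 10 in 60% of datasets. Results are descriptive, and Tables 53.031 and 53.032 would display the weight distributions. These points limit the consequences, but they do not tell the programmer which operation to run.

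**Conclusion.** The point holds as an internal inconsistency in a contingent rule. It is not a demonstrated error in the planned rates. Section 7.3.1.3 equates two operations that are not equivalent, and only the one in the parenthesis does what the rule intends.

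That an upper score cap cannot lower a BENLYSTA weight follows from the SAP's own formulas and needs no assumption. How many extreme weights survive, and how far a rate could move, depends on the assumed logit-normal score, the planned 2:1 split, and the rule being triggered. Across the SDs tried, the pooled score cap leaves 0.04 to 5.29 BENLYSTA and 0.00 to 8.10 comparator weights above 10 per dataset, against none when weights are capped at their pooled percentile. The correction is worth making before the weights are programmed, because these are the only adjusted AESI tables.

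**What to change.** Keep the existing conditions: positivity satisfied, and weights above 10 that adjusting the propensity score model cannot resolve. Delete the wording that truncates the propensity score, and state instead: *stabilized weights above the 99th percentile of the stabilized weights are set to that percentile; propensity scores are not altered.*

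State in advance whether the percentile is pooled or by exposure group. Either is acceptable. By group, with very poor overlap, a few comparator weights can stay above 10, as in the by-group comparator row of the table (0.69 and 2.43 at SD 2.0 and 2.5).

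Use these weights in Tables 54.010 and 54.020, footnote the number capped in each group, and add the step to the Appendix 10 code. The cost is one sentence, one line of code and a footnote. Capping leaves slight residual imbalance, a trade-off the SAP already accepts by planning truncation.
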